8.2.8 End-of-Study Visit (30 Days after Last Dose)

The following procedures will be performed:

- Medical and Hemophilia History (including that obtained from review of diary entries of bleeding episodes and treatment, AEs, and PRO scales)
- Concomitant medications
- Vital signs
- Diary entry of PRO scales (see **Appendix B** – EQ-5D, VAS; Haem-A-QoL; HAL)
- Physical examination
- Clinical signs of thrombosis (see **Appendix A**)
- Hematology and chemistry (see Footnote 3 for **Table 1** in **Section 1.3, Schedule of Activities**)
- Coagulation assays: PT, aPTT, fibrinogen, FVII, FVIIa activity, and TGT
- Thrombogenicity markers: D-dimer, F1+2, and TAT
- PK: MarzAA antigen and activity
- Immunogenicity assays to FVII, FVIIa, and MarzAA
- Study drug dispensing, inventory and accountability
- Adverse events

MAA-201 VERSION 2.0

8.3 STUDY ASSESSMENTS

8.3.1 Physical Examination

A full physical assessment of the major body systems will be recorded.

8.3.2 Vital signs

One measurement of blood pressure, heart rate, respiratory rate, and body temperature will be taken after the subject has been sitting quietly for at least 5 minutes.

8.3.3 Hematology

Complete blood cell count (CBC), platelet counts, and CD4 count will be measured using standard laboratory testing methods at a local laboratory.

8.3.4 Chemistry

Sodium, potassium, chloride, bicarbonate, hepatic enzymes (ALT and AST), bilirubin, albumin, blood urea nitrogen (BUN), and Cr will be measured using standard laboratory testing methods at a local laboratory.

8.3.5 Coagulation assays

PT, aPTT, fibrinogen, FVII, FVIIa activity, and TGT. These evaluations will be performed at a central laboratory.

8.3.6 Thrombogenicity markers

D-dimer, F1+2, and thrombin-antithrombin complexes (TAT). These evaluations will be performed at a central laboratory.

8.3.7 Antibody response and neutralizing antibodies to MarzAA

These evaluations will be performed and tested at a central laboratory.

8.3.8 Clinical signs of thrombosis (Appendix A)

This assessment will be included as part of the study subject training, provided as a reference on the eDiary device, and will be a scheduled evaluation at clinical study visits.

MAA-201 VERSION 2.0

8.3.9 Concomitant medications

Subjects will record concomitant medications (including name of medication, dose taken, day and time) they may be taking in their daily diaries. Diaries will be reviewed by the clinical staff at each visit.

8.3.10 ECG

A12-lead ECG will be performed using local standard methods.

8.3.11 Troponin levels

Blood troponin levels will be measured using standard laboratory testing methods at a local laboratory.

For participants that may discontinue or withdraw early, it is important to capture the rationale during the final visit. See **Section 7, Study Intervention Discontinuation and Participant Discontinuation/Withdrawal**, for details.

8.4 SAFETY AND OTHER ASSESSMENTS

Evaluations related to safety will include:

8.4.1 AEs and SAEs

Subjects will record any AEs that occur during the study in their daily diaries. Diaries will be reviewed by the clinical staff at each visit.

8.4.2 Injection site reactions

Subjects will record site injection reactions in their daily diaries. Diaries will be reviewed by the clinical staff at each visit.

Evaluations that are related to the exploratory endpoints will include the following PRO and clinician reported outcomes (ClinRO) measures:

PRO:

- Health status with the use of the EQ-5D questionnaire.⁵⁵ This is a health utility measure that includes assessment of 5 dimensions of health (mobility, self-

MAA-201 VERSION 2.0

care, usual activities, pain/discomfort, anxiety/depression) along with a 0-100 VAS.

- Haem-A-QoL, which measures the quality of life in patients with hemophilia.⁵⁶
- Hemophilia Activities List (HAL), a self-assessment which measures the perceived functional status of patients with hemophilia.⁵⁷

8.5 ADVERSE EVENTS AND SERIOUS ADVERSE EVENTS

8.5.1 Definition of Adverse Events (AE)

Definition of an AE: An AE is any untoward medical occurrence in a patient or clinical trial subject administered a medicinal product that may not necessarily have a causal relationship with this treatment. An AE can therefore be any unfavorable and unintended sign (including a clinically significant laboratory abnormality, for example), symptom, or disease temporarily associated with the use of a medicinal (investigational) product, whether or not related to the medicinal (investigational) product.

Pre-existing conditions, diseases or disorders are not considered AEs unless there is a change in the intensity, frequency or quality.

8.5.2 Definition of Serious Adverse Events (SAE)

Definition of a SAE: Definition of a SAE: An AE or suspected adverse reaction is considered "serious" if, in the view of either the investigator or sponsor, it results in any of the following outcomes: death, a life-threatening AE, inpatient hospitalization or prolongation of existing hospitalization, a persistent or significant incapacity or substantial disruption of the ability to conduct normal life functions, or a congenital anomaly/birth defect. Important medical events that may not result in death, be life-threatening, or require hospitalization may be considered serious when, based upon appropriate medical judgment, they may jeopardize the participant and may require medical or surgical intervention to prevent one of the outcomes listed in this definition. Examples of such medical events include allergic bronchospasm requiring intensive treatment in an emergency room or at home, blood dyscrasias or convulsions that do not result in inpatient hospitalization, or the development of drug dependency or drug abuse.

MAA-201 VERSION 2.0

8.5.3 Classification of an Adverse Event

8.5.3.1 Severity of Event

All AEs will be assessed by the study clinician using the CTCAE v4.0 where applicable.⁵⁹

For those AEs that are not included under the CTCAE v4.0, the following guidelines will be used to describe severity.

Mild – Events require minimal or no treatment and do not interfere with the participant's daily activities.

Moderate – Events result in a low level of inconvenience or concern with the therapeutic measures. Moderate events may cause some interference with functioning.

Severe – Events interrupt a participant's usual ADL and may require systemic drug therapy or other treatment. Severe events are usually potentially life-threatening or incapacitating. Of note, the term "severe" does not necessarily equate to "serious".

8.5.3.2 Relationship to Study Drug

All AEs must have their relationship to study drug assessed by the clinician who examines and evaluates the participant based on temporal relationship and his/her clinical judgment. The degree of certainty about causality will be graded using the categories below. In a clinical trial, the study product must always be suspect.

Related – The AE is known to occur with the study intervention, there is a reasonable possibility that the study intervention caused the AE, or there is a temporal relationship between the study intervention and event. Reasonable possibility means that there is evidence to suggest a causal relationship between the study intervention and the AE.

Not Related – There is not a reasonable possibility that the administration of the study intervention caused the event, there is no temporal relationship between the study intervention and event onset, or an alternate etiology has been established.

8.5.3.3 Action Taken

None: No changes were made to Study Drug administration and dose

Permanently discontinued: Study drug was discontinued and not restarted

MAA-201 VERSION 2.0

Temporarily interrupted, restarted same dose: Dosing was temporarily interrupted or delayed due to the AE and restarted at the same dose without unblinding to treatment group

8.5.3.4 Expectedness

The Principle Investigator (or Co-PI) will be responsible for determining whether an AE is expected or unexpected. An AE will be considered unexpected if the nature, severity, or frequency of the event is not consistent with the risk information previously described for the study intervention.

8.5.4 Time Period and Frequency for Event Assessment and Follow-Up

Subjects will be instructed regarding direct reporting and diary entries of AEs; diaries will be reviewed at each visit and subjects queried if evidence of an AE recorded.

The occurrence of an AE or SAE may come to the attention of study personnel during study visits and interviews of a study participant presenting for medical care, or upon review by a study monitor.

All AEs including local and systemic reactions not meeting the criteria for SAEs will be captured on the appropriate CRF. Information to be collected includes event description, time of onset, clinician's assessment of severity, relationship to study product (assessed only by those with the training and authority to make a diagnosis), and time of resolution/stabilization of the event. All AEs occurring while on study must be documented appropriately regardless of relationship. All AEs will be followed to adequate resolution.

Any medical condition that is present at the time that the participant is screened will be considered as baseline and not reported as an AE. However, if the study participant's condition deteriorates at any time during the study, it will be recorded as an AE.

Changes in the severity of an AE will be documented to allow an assessment of the duration of the event at each level of severity to be performed. AEs characterized as intermittent require documentation of onset and duration of each episode.

Subject Withdrawal from the Study Due to an Adverse Event:

Every reasonable effort should be made to maintain subject compliance and participation in the study. All enrolled subjects who received the study drug must

MAA-201 VERSION 2.0

be followed through the Follow-Up visit, regardless of the reason for withdrawal. If a subject who has a clinically significant laboratory abnormality or AE withdraws from the study, every effort must be made to follow these events until satisfactory resolution.

8.5.5 Adverse Event Reporting

Members of the study team will record all reportable events with start dates occurring any time after informed consent is obtained until study completion, or discharge, for non-serious AEs. At each study visit, the investigator will inquire about the occurrence of AE since the last visit. Events will be followed for outcome information until resolution or stabilization.

The Investigator will categorize the **outcome** of each AE according to the definitions below:

- Resolved: The subject recovered from the AE.
- Ongoing: At the time of the last assessment, the event is ongoing, with an undetermined outcome. Note: Ongoing AEs are not considered resolved as a result of death. No AE stop date should be recorded with an AE that is ongoing.
- Chronic/Stable: At the time of the last assessment, the event is ongoing and stabilized, with no change to the event outcome anticipated.
- Unknown: There is an inability to access the subject or the subject's records to determine the outcome (i.e., subject withdraws consent or is lost to follow-up).

All protocol-defined adverse events will be reported from the time a patient is enrolled in the study until the end of study visit.

Spontaneous or traumatic bleeding events will not be reported as an AE unless considered serious and should then be reported per the standard process for reporting.

All bleeds should be reported via the ePRO device including spontaneous bleeds, traumatic bleeds or bleeds related to procedure/surgery (see Section 7.4). Only bleeds (spontaneous bleeds, traumatic bleeds or bleeds related to procedure/surgery) that are considered serious as per definition (see Section 9.1.2) should be reported as an SAE in the CRF. Non-serious bleeds are not considered adverse events for the purpose of this protocol and should not be reported as adverse event in the eCRF.

MAA-201 VERSION 2.0

The study drug has the potential risk of causing the following AEs based on information associated with other drugs in the same category, ie, bypassing agents for treatment of hemophilia; these are:

Thrombotic events (see Appendix A)

The study drug has the potential risk of causing thrombotic events based on information associated with other drugs for treatment of hemophilia. See Appendix A for signs and symptoms listed for the subjects and the study team personnel as those requiring urgent reporting and attention.

Development of Drug Antibodies and Inhibitors

There is a risk with the study drug of developing an immune response resulting in antibody formation and potentially an inhibitory antibody response. This will also be monitored for throughout the study.

Skin injection site may become reddened or painful.

Risks associated with blood collection:

A blood draw may cause faintness, inflammation of the vein, pain, bruising, or bleeding at the site of puncture. There is also a slight chance of infection.

8.5.6 Serious Adverse Event Reporting

Members of the study team will record all reportable events within 24 hours of knowledge of the SAE with start dates occurring any time after informed consent is obtained until 30 days after the last day of study participation. At each study visit, the investigator will inquire about the occurrence of SAEs since the last visit. Events will be followed for outcome information until resolution or stabilization.

The Investigator will categorize the **outcome** of each SAE according to the definitions below:

Resolved: The subject recovered from the AE.

Ongoing: At the time of the last assessment, the event is ongoing, with an undetermined outcome. Note: Ongoing AEs are not considered resolved as a result of death. No AE stop date should be recorded with an AE that is ongoing.

MAA-201 VERSION 2.0

Chronic/Stable:	At the time of the last assessment, the event is ongoing and stabilized, with no change to the event outcome anticipated.
Death:	The AE directly caused death.
Unknown:	There is an inability to access the subject or the subject's records to determine the outcome (i.e., subject withdraws consent or is lost to follow-up).

Definitions:

Death: Any event resulting in a subject's death must be reported as an SAE. However, death, in and of itself, is not an AE; it is only an outcome. The cause of death is the AE. Therefore, the investigator should make every effort to obtain and document the cause of death for all subjects who die during the study. If, despite all efforts, the cause of death remains unknown, the AE should be documented as an "unspecified fatal event".

Life threatening AE: Any AE that places the patient or subject, in the view of the investigator, at immediate risk of death from the reaction as it occurred (*i.e.*, it does not include a reaction that, had it occurred in a more severe form, might have caused death).

Hospitalization: It should be noted that hospitalization, in and of itself, does not represent an SAE. It is the AE leading to the subject's hospitalization that becomes "serious" when it requires inpatient care. Consequently, an SAE should not be reported in the case of pre-planned hospitalizations for pre-existing conditions that did not worsen during the study.

Disability: A substantial disruption of a person's ability to conduct normal life functions.

8.5.7 Adverse Events of Special Interest (AESIs)

The study drug has the potential risk of causing the following AESIs based on information associated with other drugs in the same category. These are:

1. Thromboembolic events (TEs) based on information associated with other drugs for treatment of hemophilia. TEs include myocardial infarction (MI); venous thrombosis, and pulmonary embolism (PE); and stroke. See **Appendix A** for signs and symptoms listed for the subjects and the study team personnel as those requiring urgent reporting and attention.

MAA-201 VERSION 2.0

2. Immune response resulting in antibody formation and potentially an inhibitory antibody response. This will also be monitored for throughout the study.

8.5.8 Reporting of Pregnancy

Although pregnancy itself is not considered an adverse event or a serious adverse event, the partner of a male participant should be followed until termination or to term to ensure absence of congenital anomaly or birth defect that may have resulted from maternal exposure or transmission of the study drug via semen following paternal exposure.

Please advise all participants to use a highly effective method of birth control from the first dose of study drug through 28 days after dosing to protect the health and safety of the mother and/or child. Despite the warnings provided and precautions taken, pregnancy may occur during research participation. Investigators must be aware of the requirements related to reporting and follow-up in the event a research participant's partner becomes pregnant.

If a participant's partner becomes pregnant during this study, please provide an authorization form to present to the partner. If she is in agreement, that authorization will function as consent to approve the study doctor's access to medical information to allow the regulatory required monitoring of the pregnancy, and the birth and the health of the child.

Please report the pregnancy of a participant's partner to Catalyst Biosciences, or its designee, and the IRB, and include the following information: expected date of delivery, last menstruation, estimated conception date and pregnancy result (if known).

Pregnancy should be reported as "Information" (not as an "Adverse Event" or "Other Problem or Event").

- Pregnancy does NOT have to be reported to the IRB if the subject is receiving follow-up only, and conception occurred outside of the time period that the study protocol requires contraception (ie, 28 days after the last dose of the study drug and the pregnancy occurred after that time).
- Subsequent reports containing follow-up information regarding a pregnancy is not required unless the pregnancy results in a congenital anomaly. The congenital anomaly should be promptly reported.
- NOTE: If you suspect that exposure to a medical product prior to conception or during pregnancy may have resulted in an adverse outcome in the child, it must be reported to the FDA.

MAA-201 VERSION 2.0

9. STATISTICAL CONSIDERATIONS

With a total of 12 subjects and assuming a null hypothesis of an ABR of 12, then if the true ABR for MarzAA is 6 or less, with a one-tailed 2.5% significance level there is near 100% power to demonstrate this using a one sample Poisson test of the null hypothesis. Even if only 6 subjects were available to be pooled for this analysis, the power would still be in excess of 99%. Thus, a sample of 12 subjects is expected to provide sufficient power for the primary endpoint analysis in this study.

9.1 STUDY HYPOTHESIS

The null hypothesis (H0) is that the ABR in all subjects treated with daily SC administration of MarzAA will result in an ABR of 12 as compared to the historical control rate of 12, i.e. H0: ABR (for MarzAA) = 12. The alternative hypothesis (H1): ABR (for MarzAA) < 12.

Primary Endpoint

The primary endpoint will include:

- ABR (spontaneous and total) during Part 2 when on final MarzAA dose level versus recorded historical ABR

Bleeding events will be evaluated as follows:

- Spontaneous vs Traumatic

A spontaneous bleeding episode is defined as one that is precipitated by normal ADL.

MAA-201 VERSION 2.0

Secondary Endpoints

The secondary endpoints will include:

- Occurrence of breakthrough bleeds requiring escalation to higher dose level.
- Safety parameters: Occurrence of clinical thrombotic event not attributable to another cause, and occurrence of antibody formation resulting in a decreased endogenous level of FVII or FVIIa.
- Change in coagulation parameters (PT, aPTT, fibrinogen, MarzAA antigen and activity levels, and TGT) from pre-dose.
- Occurrence of an antibody response to MarzAA and whether it is inhibitory and cross-reactive to wt-rFVIIa or wt-FVII.
- Clinically significant levels of thrombogenicity markers resulting from daily SC administration of MarzAA
- Feasibility and ease of use of daily SC self-administration by patient as measured by compliance with treatment
- Breakthrough bleeding events will be categorized as follows:
 - Number of bleeds that are life threatening
 - Number that require hospitalization and/or blood transfusion
 - Number of muscle bleeds
 - Median time to resolution (and interquartile range) of bleeds

Exploratory Endpoints

- Identification of biomarker(s) such as antigen levels, activity levels, or global thrombosis assay evaluation that can be used to predict or correlate with a subject's lack of spontaneous bleeding.
- Identification of biomarker(s) such as D-dimer, F1+2, or a functional assay of the FVIIa activity that will identify or predict clinical thrombogenicity with the daily SC administration of MarzAA.
- Identification of biomarker(s) such as D-dimer, F1+2, or a functional assay of the FVIIa activity that will identify or predict clinical thrombogenicity of daily SC administration of MarzAA when use of rescue medication is required.
- PRO measures: EQ-5D, VAS; Haem-A-QoL; Hemophilia Activities List (HAL)

MAA-201 VERSION 2.0

9.2 SAMPLE SIZE DETERMINATION

With a total of 12 subjects and assuming a null hypothesis of an ABR of 12, then if the true ABR for MarzAA is 6 or less, with a one-tailed 2.5% significance level there is near 100% power to demonstrate this using a one sample Poisson test of the null hypothesis. Even if only 6 subjects were available to be pooled for this analysis, the power would still be in excess of 99%. Thus, a sample of 12 subjects is expected to provide sufficient power for the primary endpoint analysis in this study.

12 subjects were chosen to increase the size of the safety data set.

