
Statistics
 
Primary Analysis Plan:
 
Standard pharmacokinetic parameters, such as terminal half-life, AUC_{0-t}, clearance, mean residence time and volume of distribution will be calculated. In addition, the bioavailability of the SC administration will be computed. Descriptive statistics for these parameters will be reported. The number of subjects requiring dose escalation will be reported.
 
The analysis of the primary endpoint (ABR) of the final dose used to treat a subject will be based on the evaluation of the ABR of MarzAA compared to a rate for on-demand therapy. The latter is assumed to be 12, ie, 1 bleed per month, as our null hypothesis (H₀). The comparison of the actual ABR for MarzAA either pooled across all doses used or evaluated at the highest dose for an individual will be compared to this null hypothesized value using the one-sample test for a Poisson rate (using an exact calculation of the p-value). Because this will be a one-tailed test (the alternative hypothesis [H₁] is the ABR for MarzAA will be < 12), a one-tailed 2.5% significance level will be used.

Rationale for Number of Subjects:
 
With a total of 12 subjects and assuming a null hypothesis of an ABR of 12, then the demonstration of a reduction to an ABR of 6 or less with a one-tailed 2.5% significance level would be accomplished with near 100% power using a one sample Poisson test of the null hypothesis. Even if only 6 subjects were available to be pooled for this analysis, the power would still be in excess of 99%.

Name of sponsor: Catalyst Biosciences

MAA-201 VERSION 2.0

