### 3.5 DETERMINATION OF SAMPLE SIZE

With a total of 12 subjects and assuming a null hypothesis of an ABR of 12, then if the true ABR for MarzAA is 6 or less, with a one-tailed 2.5% significance level there is near 100% power to demonstrate this using a one sample Poisson test of the null hypothesis. Even if only 6 subjects were available to be pooled for this analysis, the power would still be in excess of 99%. Thus, a sample of 12 subjects is expected to provide sufficient power for the primary endpoint analysis in this study.

Twelve subjects were chosen to increase the size of the safety data set.

If a subject does not complete the study as defined in the protocol (i.e., before receiving study drug for 50 days at the same dose level) another subject will need to be enrolled in replacement.

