### 8.1 PRIMARY EFFICACY ENDPOINT AND ANALYSIS

#### 8.1.1 Primary Efficacy Endpoint

The analysis of the primary endpoint (annualized bleeding rate (ABR) for spontaneous and traumatic bleeds) under the final treated dose of MarzAA for each subject will be based on the one sample test compared to a pre-defined rate assumed for the on-demand therapy. The pre-defined rate is assumed to be 12 bleeds in total (i.e. one bleed per month), defined as the minimum ABR for each subject according to inclusion criterion 2 (defined as the null hypothesis (H0)). The comparison of the actual ABR for MarzAA at the highest dose for an individual will be performed using the one-sample test for a Poisson rate versus the pre-defined margin of 12 (using an exact Poisson regression model in SAS 9.4). A one-tailed 2.5% significance level will be used For the following hypothesis test:

$$H_0: ABR_{\text{MarzAA}} \geq 12 \text{ versus } H_1: ABR_{\text{MarzAA}} < 12.$$

The ITT population will be used for the statistical analysis of the primary efficacy endpoint.

In order to calculate the ABR for subjects who do not have a total of 12 months of follow up, the ABR will be calculated as:

$$(\text{Number of bleeds/number of months on study}) \times 12$$

Note: number of months is calculated as the exposure (in days) at each dose level / 30.5.

Formally, assume that the hypothesis is: H0:  $\lambda = \lambda_0$  vs Ha:  $\lambda < \lambda_0$ . Let n be the number of subjects, we can calculate the critical point Ncrit which is the largest integer meeting

$$\sum_0^{N_{crit}} e^{-n\lambda_0} \frac{(n\lambda_0)^k}{k!} \leq \alpha \quad (1)$$

If the total number of bleeds during the final MarzAA dose for all subjects is less than Ncrit, then the null hypothesis is rejected.

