**Statistical Analysis Plan**

Catalyst Biosciences, Inc. Protocol # MAA-201

Version 2.0

Syneos Health #1009647

In order to compare ABR (spontaneous and total) during part 2 when on final MarzAA dose level with the actually recorded historical data, a Poisson regression model using PROC GENMOD procedure will be used with the ABR as the dependent variable, intercept as the independent variable and log e transformed of 12 will be used as offset variable. An example SAS code has been provided in [Appendix I](#).

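### The stated power and the SAP primary test both count each subject as one year of observation, but planned exposure at the final dose is 50 days

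*Protocol*

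**What the plan says.** **Power.** SAP 3.5 states that "with a one-tailed 2.5% significance level there is near 100% power to demonstrate this using a one sample Poisson test", for a null ABR of 12 and a true ABR of 6 or less with 12 subjects. The Protocol 1.1 synopsis says this "would be accomplished with near 100% power using a one sample Poisson test of the null hypothesis". Protocol 9 and 9.2 repeat the claim and add "Even if only 6 subjects were available to be pooled for this analysis, the power would still be in excess of 99" percent. Section 9 concludes: "Thus, a sample of 12 subjects is expected to provide sufficient power for the primary endpoint analysis in this study". None of these sections states a follow-up time.

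**Exposure.** The primary endpoint is ABR in Part 2 on the final dose level (Protocol 9.1, SAP 4.1). Protocol 4.2 requires 50 days without spontaneous bleeding on one of the first three levels, or 50 days of treatment on the fourth. All Part 2 dosing is capped at 197 days (Protocol 1.1 and 4.2).

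**Test.** SAP 8.1.1 says: "Let n be the number of subjects, we can calculate the critical point" (Ncrit), using a Poisson mean of n × λ0. It then rejects by this rule: "If the total number of bleeds during the final MarzAA dose for all subjects is less than" Ncrit. The accompanying GENMOD model is specified "with the ABR as the dependent variable, intercept as the independent variable and log e transformed of 12 will be used as offset variable", and the Appendix I code does the same. Exposure appears only when each subject's ABR is computed: "number of months is calculated as the exposure (in days) at each dose level / 30.5".

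**The concern.** The information in a one-sample Poisson rate test is the expected number of events, which is rate × person-time. A power figure built from the number of subjects and an annual rate alone implicitly gives every subject one year. Twelve subjects at 50 days supply 600 subject-days, about 1.64 person-years instead of 12.

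For the sample size text the result is an overstated power. The SAP test is the more serious matter. If its critical value is built for 12 person-years and applied to bleeds from 1.64, it no longer tests an ABR of 12 at the 2.5% level, and an ineffective drug could be declared effective.

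**Working it through.** **Inputs.** Null ABR 12, alternative 6, one-sided α = 0.025, 12 or 6 subjects (Protocol 9.2, SAP 3.5). Exposure is 50 days at the final dose and at most 197 days in Part 2 (Protocol 1.1, 4.2). The SAP's 30.5-day month makes a year 366 days; a 365-day year is shown as well because the cutoff is discrete.

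**Formula.** With n subjects and T years each, c is the largest integer with P(X ≤ c | 12nT) ≤ 0.025. Power is P(X ≤ c | 6nT).

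**1. Reproducing the plan's figures (T = 1 year)**
- 12 subjects: null mean 12 × 12 = 144, c = 120, power above 99.999%.
- 6 subjects: null mean 6 × 12 = 72, c = 55, power 99.88%.

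Both match the stated figures.

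**2. Power at planned exposure, ABR 6**

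| Exposure per subject | n | Null mean | c | Type I error | Power |
|---|---|---|---|---|---|
| 50 days, 366-day year | 12 | 19.67 | 10 | 1.3% | 60% |
| 50 days, 365-day year | 12 | 19.73 | 11 | 2.4% | 71% |
| 50 days, either year | 6 | 9.8–9.9 | 3 | 1.1–1.2% | 27–28% |
| 197 days, either year | 12 | 77.5–77.7 | 60 | 2.2–2.3% | 99.9% |
| 197 days, either year | 6 | 38.8–38.9 | 26 | 1.9–2.0% | 94% |

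With 12 subjects at 50 days, power is 80–87% at ABR 5 and 93–96% at ABR 4. Power of at least 99% at ABR 6 needs about 142 days each with 12 subjects, or about 283 days each with 6.

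**3. SAP equation (1), 12 subjects, 50 days each.** With n = 12 and λ0 = 12, Ncrit = 120. Expected final-dose bleeds at ABR 12 are 12 × 12 × 50/366 ≈ 19.7.
- P(count < 120) is about 1 at ABR 12.
- At ABR 60 about 98 bleeds are expected, and P(count < 120) is still 98%.
- The expected count reaches 120 only at an ABR of about 73 (120 ÷ 1.64).

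**4. SAP GENMOD model, 12 subjects, 50 days each.** One bleed enters as 366/50 = 7.32 (7.30 with 365 days), while the offset ln(12) still treats the subject as one year.
- 16 bleeds enter as 116.8–117.1, below the cutoff of 120. 17 enter as 124.1–124.4, above it.
- The rule therefore rejects at 16 or fewer observed bleeds.
- P(X ≤ 16) at a mean of about 19.7 is 23.9–24.3%, against a nominal 2.5%.

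**5. The inequality.** Ncrit is defined as the largest count whose cumulative probability is at most α, so the count Ncrit itself belongs in the rejection region. Rejecting only below Ncrit, after the exposure correction, would lower power at ABR 6 from 60–71% to 48–60%.

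**The case against.** - **λ0 has no number in equation (1).** If it meant expected bleeds per subject over the final-dose period (12 × 50/366 = 1.64), the rule would be coherent. This is a fair textual point, so the result in step 3 depends on the annual reading. But SAP 8.1.1 sets the null at an ABR of 12 immediately above the equation, and the model's offset is ln(12). The step 4 result does not depend on equation (1) being read that way.
- **One year per subject is inferred.** It is. However, it reproduces both figures, and no planned exposure reproduces the 6-subject one.
- **The protocol also allows pooling across doses.** A simulation of the escalation rule (dose-independent rate, 70–100% of bleeds spontaneous, no dropout; both are assumptions) gives mean Part 2 exposure of about 66–74 days at ABR 6. Pooled power with 12 subjects is then 84–89%, at a level of about 2%. So 60–71% belongs to the final-dose test, which is the one the SAP adopts. Near 100% for 12 subjects would hold only in the extreme case of 197 pooled days for everyone.
- **60% partly reflects discreteness.** With a 366-day year, 51, 52 and 53 days give 69%, 67% and 65%. The range should be quoted, not the single lowest value.
- **24% is not this trial's actual error rate.** Correct. It assumes a fixed 50 days with no escalation. Under the same simulation at a true ABR of 12, the exposure-corrected final-dose test still rejects 52–65% of the time and the annualised rule about 93%, because final levels below the maximum are selected for absence of spontaneous bleeds.
- **Six subjects is hypothetical and 12 was chosen for safety data.** True, and non-completers are replaced. That limits the harm of the power sentence, not of the test.

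**Conclusion.** The concern holds. The stated power reproduces only at about one year per subject. At the planned 50 days it is 60–71% with 12 subjects and 27–28% with 6, and the 6-subject claim fails at every planned exposure. The primary test in SAP 8.1.1 and Appendix I omits the same exposure term. At a fixed 50 days its type I error is about 24% for the annualised model, and close to 1 for equation (1) on the annual reading.

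These figures assume a homogeneous Poisson process and fixed exposure, without overdispersion. They compare the written rules with a correct exposure-based test and do not give the operating power of the final-dose analysis, which selection of the final dose also distorts. This must be fixed before analysis, mainly because of the SAP test; the power sentence alone would be a lesser correction.

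**What to change.** 1. **Protocol 1.1, 9, 9.2 and SAP 3.5:** state the person-time, restate the power and delete the 6-subject sentence. For example:

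   > Assuming 12 subjects with 50 days each at the final dose level (600 subject-days, 1.64 person-years), an exact one-sided 2.5% Poisson test of ABR 12 has power of 60–71% at a true ABR of 6, 80–87% at 5 and 93–96% at 4 (366-day to 365-day year).

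2. **SAP 8.1.1, equation (1):** replace n by total person-years at the final dose, define λ0 as 12 per person-year, and reject when the count is less than or equal to Ncrit. At 50 days each, Ncrit becomes 10–11, with type I error of 1.3–2.4% under fixed exposure.
3. **SAP 8.1.1 model and Appendix I:** use the observed bleed count as the response, with offset ln(12 × person-years), where person-years = final-dose exposure days / 366 under the SAP's own month convention.
4. **Beside the restated power:** note that it is a fixed-exposure benchmark and that selection of the final dose is a separate issue these changes do not solve. The pooled analysis the protocol already names can be reported alongside.

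**Cost:** text edits in both documents and a one-line code change. Endpoint, enrolment and conduct stay as they are. The stated power becomes less favourable, and the test becomes harder to pass (10–11 bleeds at 50 days each, instead of 16 or 120).
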